Figure 5 (left): Proportions of in-hospital mortality and independent functional status among survivors over increasing oxygen tensions. We found linear trends for increasing mortality and decreasing functional independence with increasing oxygen tension, $p < 0.0001$.

Figure 6 (right): Odds ratios (solid line) and 95% confidence intervals (dotted lines) for in-hospital death with increasing increments of oxygen tension.

C.3.3. Development of a clinical protocol for rapid FiO₂ optimization.

The method of rapid FiO₂ optimization in REOX II must be comprised of a detailed protocol (see *Methods* section below) rather than a simple directive to titrate FiO₂ to keep SaO₂ or PaO₂ in a predetermined range, because rigorous uniformity is needed in the approach across all study sites, including uniformity in the increments and frequency of FiO₂ reductions. The therapeutic goal of our protocol is a PaO₂ of 60-99 mmHg, because this is the PaO₂ range that was associated with the lowest risk of poor outcome in our previously published work.²⁵ We also use PaO₂ (measured by arterial blood gas [ABG] analysis) as the ultimate goal rather than SaO₂ measured by pulse oximetry because an SaO₂ value <100% on pulse oximetry monitoring does not always exclude supranormal PaO₂. The protocol in this application begins with very rapid reduction of FiO₂ as much as possible according to SaO₂ values, and when FiO₂ is maximally reduced by SaO₂ an ABG is measured, followed by finer adjustment of FiO₂ to achieve a PaO₂ 60-99 mmHg. The protocol must not only prescribe each downward titration of FiO₂ but it must also include detailed limbs for *upward* titration of FiO₂ to account for potential “overshoot” in FiO₂ reduction. We acknowledge that the flowchart for FiO₂ titration in the *Methods* section (**Figure 9**) may appear complex, but our experience is that this level of detail is needed in order to ensure that FiO₂ optimization will not only be rapid and effective, but also safe. We believe using this protocol will allow for rapid achievement of the target PaO₂ after ROSC and no significant hypoxic events related to overshoot.

C.3.4. Optimal assessment of oxidative stress *in vivo*.

Roberts LJ, and colleagues. Biomarkers of Oxidative Stress Study II: Are oxidation products of lipids, proteins, and DNA markers of CCL₄ poisoning? *Free Radic Biol Med* 2005;38(6):698-710.

[figure not shown]

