C.3.7. Neuropsychological deficits among survivors of out-of-hospital cardiac arrest.

[figure not shown]

This NIH-funded (R01HD046442) prospective study determined the nature and severity of residual cognitive deficits for survivors of OHCA. Thirty OHCA patients who recovered alertness within 1-3 days of ROSC but remained confused at one week, and 30 non-OHCA coronary care admissions (matched controls) were administered neuropsychological testing at 90 days in five cognitive domains: memory, executive function, lexical-semantic, visuoperceptual, and psychomotor (**Figure 8**). Subjects fell into two deficit profiles. Two-thirds had only mild memory deficits and borderline psychomotor deficits compared to controls; 40% in this mild group had returned to work. The other one-third of patients had severe impairments in all domains. In the severe group, only as impairment in memory or psychomotor

domains increased did impairments in other domains appear. Follow-up evaluation at one year revealed discouraging little further cognitive improvement over the levels reached at 90 days. Only one additional subject returned to work. In addition, we assessed health-related quality of life (QOL) at one year using the Sickness Impact Profile-68 (SIP-68)⁴⁴, a measure of health-related functional status in rehabilitation medicine, and found that the OHCA patients reported more adverse effects on health than the cardiac control patients due to poorer psychological health and social participation, not due to effects on physical health.

The proposed study will use a similar methodology for neuropsychological testing and functional assessment at 180 days after resuscitation among survivors.

Figure 8: Composite z-scores – mean and standard deviation – for neuropsychological function in five cognitive domains among cardiac controls (CC), all out-of-hospital cardiac arrests (OHCA), and mild and severely impaired OHCA patients separately. Deficits after OHCA were most common and most severe in memory and psychomotor domains.

D.1. RESEARCH DESIGN AND METHODS

D.1.1 Specific Aims

We will test if a protocol for rapid FiO₂ optimization following ROSC from cardiac arrest is associated with:

- *Reduced in vivo oxidative stress during the post-resuscitation phase of therapy (Aim 1)*

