- *Reduced neurological disability at hospital discharge (Aim 2)*
- *Reduced neuropsychological and functional deficits among survivors at 180 days (Aim 3)*

D.1.2. Overview

Design: Prospective protocol implementation study with an observational comparison group [REOX II (intervention component) versus REOX I (observational component)]

Participants: Adult patients resuscitated from cardiac arrest

Enrollment location: Emergency Departments of 6 urban academic medical centers

Intervention: Implementation of a clinical protocol for rapid FiO₂ optimization after ROSC from cardiac arrest.

Primary outcome: Good neurological outcome (defined as Modified Rankin Scale ≤ 3 ⁴⁵ at hospital discharge).

Secondary outcomes: Neuropsychological tests and ability to return to work among survivors at 180 days.

Mechanistic outcomes: Oxidative stress markers (IsoPs/IsoFs) in plasma 0-6 hours after ROSC.

Estimated sample size and study duration: 280 patients (205 from REOX I and 75 from REOX II).

[figure not shown]
D.2. REOX II Study Protocol

Study setting and population: This study is the second phase in a two-phase study. The initial phase, REOX I, was an observational-only study. As in REOX I, REOX II will identify subjects with return of spontaneous circulation (ROSC) after cardiac arrest in 6 hospitals (Cooper University Hospital, Camden, NJ; Hospital of the University of Pennsylvania and Penn-Presbyterian Medical Center, both in Philadelphia, PA; University of Mississippi Medical Center, Jackson, MS; Methodist Hospital, Indianapolis, IN; and Beth Israel Deaconess Medical Center, Boston, MA). The inclusion criteria are: age > 17 years; cardiac arrest; ROSC achieved; comatose (Glasgow Coma Scale motor score < 6) after ROSC; and clinician intent to treat with target temperature management. The exclusion criteria are: presumed etiology of arrest is trauma, hemorrhage or sepsis; resident of a nursing home or other long-term care facility; known or clinically apparent pregnancy; known lack of commitment to aggressive support by next of kin; and any other condition, that, in the opinion of the investigator, would preclude the subject from being a suitable candidate (e.g. end stage chronic illness with no reasonable expectation of survival to hospital discharge).

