Patient identification and recruitment: Each of the participating centers currently has a mechanism in place for real-time notification of study personnel when an OHCA subject arrives in the emergency department (ED) or when a cardiac arrest occurs in-hospital. Each center has previously validated its notification mechanism to ensure that subjects will not be missed and the population of potentially eligible subjects will be consecutive cardiac arrest subjects. Study personnel will assess patient eligibility and will immediately enroll subjects meeting all inclusion and no exclusion criteria.

Informed consent: In line with REOX I (observational-only component), in REOX II we will begin initial collection of cardiac arrest and post-resuscitation data immediately after ROSC. As per the inclusion criteria all subjects will be comatose during the initial post-ROSC period and therefore will not be able to consent themselves for the study intervention (i.e. protocol for rapid FiO₂ optimization after cardiac arrest). Once a subject is identified to have all inclusion and no exclusion criteria, we will approach surrogates (i.e. next of kin or legally authorized representative)

Figure 9 Flow diagram for enrollment

[figure not shown]
within the first four hours after ROSC for written informed consent and HIPAA authorization prior to implementation of the study intervention. If communication with a surrogate within the first four hours after ROSC is not achieved the subject will not be eligible for the study intervention. However, for subjects who are excluded from the study intervention due to lack of informed consent within the first four hours after ROSC, we will approach subjects or surrogates at a later time for written informed consent and HIPAA authorization for participation in the observational only (REOX I) component of the study including (a) use of plasma samples for research purposes (both stored samples obtained at the time of initial resuscitation and new samples); (b) determination of Modified Rankin Scale at hospital discharge; and (c) follow-up visits for neuropsychological testing at 180 days (**Figure 9**).

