Therapeutic interventions: **Table 3** displays the standard elements of post-resuscitation care across all centers. All sites are experienced in target temperature management after ROSC and target 32-36°C for 24 hours using external cooling devices (Arctic Sun, Medivance, USA, or Gaymar III, Gaymar Industries, USA). Using a standardized order set for target temperature management induction, we demonstrated successful achievement of target temperature in 96% of patients and a median time from ROSC to target temperature of four hours (i.e. faster than the landmark randomized trial) in our routine clinical care.⁴⁰ All standard elements in **Table 3** reflect current AHA recommendations.¹² All subjects in this study will receive standard post-resuscitation care. Since none of the sites previously had a protocol in place for FiO₂ titration after ROSC and our standardized order sets for post-resuscitation care do not have orders for FiO₂ titration, subjects in REOX I (observational only component) had clinician-directed FiO₂ titration after ROSC.

For the interventional component of this study we will implement the protocol for rapid FiO₂ optimization after cardiac arrest (**Figure 10**) at all sites. Once a subject is identified and written informed consent is obtained from a surrogate, the study intervention (i.e. rapid FiO₂ optimization protocol) will be activated by the investigator who receives notification in real-time. (see “*Patient identification and recruitment*” above). The on call investigator will communicate directly with the clinical care team at the bedside and will ensure activation and adherence to the clinical protocol. Subjects enrolled in the study intervention will receive standard post-resuscitation care in **Table 3** *plus* rapid FiO₂ optimization according to **Figure 10**. Our sites have an outstanding track record of sustained clinical adherence to new resuscitation protocols for multi-year time periods.³⁷⁻⁴² Subjects who are excluded from the study intervention due to lack of informed consent within the first four hours after ROSC, will still be eligible for the observational only aspect of this study (REOX I). These subjects will receive standard post-resuscitation care outlined in **Table 3**, but will not have activation of the rapid FiO₂ optimization.

Table 3: Standard elements of post-cardiac arrest care across all centers. (TH = therapeutic hypothermia; GCS = Glasgow Coma Scale; ROSC = return of spontaneous circulation)

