Data collection: We will collect baseline data (e.g. demographics, comorbidities, etc.) and intra-arrest data (e.g. location, initial rhythm, length of downtime, etc.) using the Utstein template for cardiac arrest research⁴⁶ including the recommended variables for post-resuscitation research.⁴⁷ We will capture multiple indicators of post-resuscitation care quality in accordance with the 2010 AHA guidelines.¹² As mandated by the protocol (**Figure 10**) above, our standardized order set for post-resuscitation care will include multiple arterial blood gas (ABG) analyses for partial pressure of arterial oxygen (PaO_2) measurement after ROSC. As part of standard care each institution already obtains ABG analyses at 0- and 6-hours after ROSC. Any additional ABG analyses required to achieve the PaO_2 goal described in **Figure 10** will be considered for research purposes and will be funded by the study. We will record all ABG results over the initial 36 hours after ROSC. We will capture SaO_2 continuously for the initial 36 hours after ROSC. We will also capture every adjustment in FiO_2 from respiratory therapy records and the precise time of the adjustment. We will obtain plasma samples after ROSC at 0- and 6-hours after ROSC and ship the samples to the laboratory of our collaborator [name] (Vanderbilt) for measurement of isoprostanes (IsoPs) and isofurans (IsoFs) by gas chromatography negative ion chemical ionization mass spectrometry (GC/NICI/MS). IsoP and IsoF assays are remarkably stable and therefore are applicable to stored specimens. We can measure IsoPs and IsoFs on clinical plasma samples obtained immediately after ROSC because (after informed consent is secured) we can use samples left over in the clinical laboratory that are routinely discarded.

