Secondary analyses: We will compare proportions of good neurological outcome [defined as a mRS ≤ 3 (based on the preliminary data of our collaborator, [name], University of Pittsburgh)],⁴⁵ between subjects who receive the study intervention (i.e. rapid FiO₂ optimization) vs. those who do not receive the study intervention, using binomial test. Among survivors, we will compare the 180-day neuropsychological measures (composite z-scores for each cognitive domain) between the same two groups using t-test or Mann-Whitney U as appropriate with corrections for multiple comparisons. We will compare the proportions of patients able to return to work between the two groups using binomial test. We will compare plasma IsoPs/IsoFs at each time point between the two groups using t-test or Mann-Whitney U as appropriate with corrections for multiple comparisons.

Sample Size: The sample size calculation in the initial study proposal was based on the primary outcome, mRS at hospital discharge, and we planned to enroll a total of 266 subjects. To ensure adequate power to test the relationships between the above independent variables and cognitive domains, we assumed a medium relationship strength between the six independent variables and each of the five cognitive domains ($R^2 = 0.15$). In order to achieve 80% power and an $\alpha = 0.05$ we would require a minimal of 85 subjects to undergo neuropsychological testing at 180 days. This sample size will be among the largest prospective studies of

neuropsychological outcomes that we are aware of in the literature.^{8,29-32} Assuming a 15% drop out rate for lost to follow up for neuropsychological testing at 180 days we would require 98 subjects to be discharged with a mRS \leq 4. Based on preliminary data from REOX I we expect 35% of patients will be discharged with a mRS \leq 4 and undergo cognitive testing at 180 days. We would therefore require a minimal total sample size of 280 subjects between REOX I and II combined for the multivariable testing. We have enrolled 200 subjects in REOX I to date. We anticipate additional subjects to be enrolled in REOX I and therefore plan for 75 subjects to be enrolled in REOX II to ensure a total sample size of at least 280 subjects.

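### The only oxidative-stress sample that can show an effect of the protocol is at 6 hours after ROSC, but activation may come as late as about 4 hours, so the Aim 1 contrast may be diluted and a null result would be ambiguous

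*Combined protocol and SAP*

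**What the plan says.** Aim 1 (D.1.1 Specific Aims) asks whether the rapid FiO₂ protocol is associated with less oxidative stress in the post-resuscitation phase. It sets no time limit. D.1.2 Overview narrows the outcome to "Oxidative stress markers (IsoPs/IsoFs) in plasma 0-6 hours after ROSC". Under Data collection in D.2 the draws are timed from ROSC: "We will obtain plasma samples after ROSC at 0- and 6-hours after ROSC". No later isoprostane or isofuran sample is listed.

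The intervention is timed from consent. Under Informed consent, surrogates are approached "within the first four hours after ROSC for written informed consent and HIPAA authorization prior to implementation of the study intervention". The limit is on reaching them: "If communication with a surrogate within the first four hours after ROSC is not achieved the subject will not be eligible for the study intervention". Therapeutic interventions gives the same order: "Once a subject is identified and written informed consent is obtained from a surrogate, the study intervention" is then activated. C.3.3 describes stepwise titration after activation: "when FiO₂ is maximally reduced by SaO₂ an ABG is measured, followed by finer adjustment". Time to target is not stated in the text, and Figure 10 is not available to check.

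Under Secondary analyses the marker test is a plain two-group comparison: "We will compare plasma IsoPs/IsoFs at each time point between the two groups", by t-test or Mann-Whitney U with a multiplicity correction. Activation time appears nowhere in the Analysis section. The only PaO₂ summary there is a 24-hour time-weighted average (TWA), used for the mRS and the cognitive domains.

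**The concern.** Sampling is anchored to ROSC and the intervention to consent, and no analysis deals with the gap. Two consequences follow.

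- The 0-hour comparison cannot show an effect of the protocol, because consent must come first. It can show only whether the groups started alike.
- At 6 hours, a patient activated soon after ROSC and one activated near 4 hours count as equally treated. The second had clinician-directed oxygen for about two thirds of the interval that the sample covers.

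A null 6-hour comparison could therefore mean that the protocol does not lower oxidative stress, or that much of the interval passed before it started. The plan offers no way to tell these apart.

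The plan's own material points to closer matching. In the neonatal trial described in C.3.6, the oxygen contrast began at delivery and isofurans were followed over the first day. The plan also splits its organ-failure score into 0-6 and 6-36 hours, but has no 0-6 hour oxygen summary to set beside the 6-hour marker.

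**Working it through.** **The plan's own figure.** No effect size, power or sample size is stated for Aim 1. The chain under Sample Size serves the 180-day cognitive regressions: 85 tested, 85 × 1.15 = 97.75, so 98 discharged with mRS ≤ 4, and 98 / 0.35 = 280. It reproduces but does not bear on the markers.

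**Inputs from the documents.** Draws at 0 and 6 h (Data collection); consent limit 4 h (Informed consent); 205 REOX I and 75 REOX II subjects (D.1.2).

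**Assumptions, none of them in the documents.** The 6-h group difference is proportional to hours on protocol; a full-window effect is 0.5 SD; every subject has a 6-h sample; all REOX II subjects start at the same hour; the test is two-sided 5% with no multiplicity correction.

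**Step 1: share of the window on protocol.** Share = (6 − start hour) / 6.

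**Step 2: power.** The standard error of a standardised difference is √(1/75 + 1/205) = √(0.01333 + 0.00488) = 0.135. Power ≈ Φ(0.5 × share / 0.135 − 1.96).

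| Start for all (h) | Share on protocol | Difference (SD) | Power |
|---|---|---|---|
| 0 (undiluted) | 6/6 = 100% | 0.50 | 96% |
| 1 | 5/6 = 83% | 0.42 | 87% |
| 2 | 4/6 = 67% | 0.33 | 70% |
| 3 | 3/6 = 50% | 0.25 | 46% |
| 4 | 2/6 = 33% | 0.17 | 23% |

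The smallest difference detectable with 80% power is (1.96 + 0.84) × 0.135 = 0.38 SD.

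**Step 3: titration lag.** If titration takes 0.5 to 1 h (assumed), a 4-h start leaves 1.5 to 1 h on target, or 25% to 17% of the window.

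**Step 4: when clinician-set oxygen fills more than half the window.** This needs (6 − start − lag) / 6 < 0.5, so start > 3 − lag: after 3 h with no lag, or after 2 h with a 1-h lag. If starts were spread evenly over 0-4 h (assumed), the mean share would be (6 − 2) / 6 = 67%, and one patient in four would start after 3 h.

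**Step 5: multiplicity.** The plan corrects for multiple comparisons but does not name the method. With Bonferroni over four tests (two markers, two times; assumed), alpha is 0.0125 and the critical value 2.50. Power falls to about 89% undiluted, 49% for a 2-h start and 26% for a 3-h start. The detectable difference rises from 0.38 to 0.45 SD. If only the two 6-h tests are corrected (alpha 0.025) it is 0.42 SD, so the 0-h tests use up alpha without being able to show an effect.

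**The case against.** The strongest reply has four parts.

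1. **Four hours is a ceiling, not a typical start.** A reader might infer that the 6-hour marker mostly reflects clinician-set oxygen. The documents do not support that. By the arithmetic above it is true only for starts after 3 hours, or after 2 hours with an assumed 1-hour lag, and no start-time distribution is given. Kinetics are not given either. If the markers clear quickly, a 6-hour level weights recent, on-protocol hours and the dilution is smaller.

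2. **The test is not empty.** A reader might also infer that a null result would not test the protocol at all. Patients activated within about 4 hours have about 2 to almost 6 hours of protocol before the draw. The declared intervention is implementation of a clinical protocol, with the consent delay built in. For that question the unstratified comparison is legitimate and should stay.

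3. **The 24-hour average is not an error.** The plan never pairs TWA-PaO₂ with the markers. The gap is that no exposure summary is matched to them, although the raw data are collected.

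4. **Extra analyses do not move the sample.** This stands. They help to interpret the result but do not remove the dilution. A later draw would act on timing directly, but about 200 REOX I subjects are already enrolled, and a new draw time in REOX II might have no counterpart among them.

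A rule that a null counts only if an early-activated subset agrees would also be unsound. It is one-sided, with no matching condition on a positive result, and it rests on a selected group. With even starts over 0-4 hours, the set activated by 2 hours is about 37 patients with a mean share of 83%. Power is then Φ(0.417 / √(1/37 + 1/205) − 1.96), about 65%, against about 70% for the overall test at the mean share of 67%.

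**Conclusion.** The point holds as one of dilution and ambiguity. The documents establish three facts: the only post-intervention marker sample is at 6 hours after ROSC; activation may come up to about 4 hours after ROSC; and the planned comparison ignores the interval between them. The 6-hour sample may thus follow as little as about 2 hours of protocol, less titration time.

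How much this costs is unknown. The power figures are illustrations resting on assumed proportionality, an assumed 0.5 SD effect, complete sampling and a common start time. The 23% figure needs every patient to start at the ceiling. This concerns a mechanistic aim, not the primary outcome.

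**What to change.** Keep the overall 6-hour group comparison as planned, and label the 0-hour comparison a baseline check. Record activation time for every REOX II subject. Prespecify two supportive analyses:

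- (a) a regression of the 6-hour isoprostane and isofuran levels on TWA-PaO₂ over 0-6 hours, in both components, with the plan's five covariates;
- (b) within REOX II, the 6-hour marker against hours from activation to the draw, as a continuous variable.

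Report the distribution of activation times beside the overall result, and describe a null overall result as applying to the protocol as implemented with that delay. Add no rule that makes a null count only if the supportive analyses agree.

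**Cost:** one time field and analysis-plan wording, with no new draws or patients. Under Data collection the study already records all blood gases to 36 hours, and each FiO₂ change with its time.

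**Downsides to state in the plan:** both analyses are non-randomised. Early activation is selected by fast surrogate contact. Standard care provides blood gases at 0 and 6 hours while the protocol may add more, so the 0-6 hour average may be measured less precisely in REOX I than in REOX II.

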These data from animal models support the hypothesis that hyperoxia after ROSC may worsen outcomes in post-resuscitation patients. However, clinical data are few. Three preliminary retrospective multi-center analyses have been published. Two of these were published by our research team.^{24,25} In a large (n=6326) cohort of patients admitted to one of 120 U.S. ICUs after cardiac arrest, we found that post-ROSC hyperoxia was **common, an independent predictor of in-hospital death, and associated with lower functional independence among survivors.**²⁴ In a secondary analysis using the same ICU database, we found that a linear, **“dose-dependent” relationship exists between supranormal PaO₂ after ROSC and mortality**²⁵ (see *Preliminary Studies* in sections C.3.1 and C.3.2). However, a recent study from the Australian and New Zealand Intensive Care Society (ANZICS) investigators reported somewhat different results.²⁶ Using a retrospective methodology that replicated our initial study, they found that among 12,000 patients admitted to an ICU after cardiac arrest, patients with hyperoxia (defined by our previous methodology as a PaO₂ >300 mmHg) had significantly higher mortality (59% [95%CI 56-61%]) than patients with normoxia (47% [95% CI 45-50%]), but not patients with hypoxia (60% [95% CI 59-61%]). In a multivariable model adjusting for illness severity, hyperoxia had an odds ratio for mortality of 1.2 (95% CI 1.1-1.6). However, when statistical models with a number of additional adjustments were applied, the association with increased mortality was lost. They concluded that hyperoxia has no consistently reproducible independent association with mortality.²⁶ Therefore, **whether hyperoxia is associated with poor outcome in post-resuscitation patients remains unclear.** Given that post-ROSC hyperoxia exposure is extremely common²⁵, this unanswered question represents a **critical knowledge gap** for resuscitation science. Accordingly, this project will generate **new, critically important knowledge about a fundamental element of post-cardiac arrest care.**

[figure not shown]
B. INNOVATION

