Using Project IMPACT, a database of ICU admissions from 120 U.S. hospitals, we tested the hypothesis that exposure to hyperoxia (defined as a PaO₂ \geq 300 mmHg on the first arterial blood gas recorded in the ICU) was associated with increased in-hospital death among 6326 patients admitted to an ICU after cardiac arrest. We found that the patients with hyperoxia had significantly higher in-hospital mortality (63% [95% CI 60%-66%]) compared to patients with normoxia (45% [95% CI 43%-48%]; proportion difference 18% [95% CI 14%-22%]), and also compared to patients with hypoxia (57% [95% CI 56%-59%]; proportion difference, 6% [95% CI, 3%-9%]). Survival over time appears in **Figure 4**. In a model controlling for potential confounders (e.g., age, preadmission functional status, comorbid conditions, vital signs, and other physiological indices) including sensitivity analyses that adjusted for hospital factors and propensity of hyperoxia exposure, hyperoxia had an odds ratio for death of 1.8 (95% CI, 1.5-2.2).

Among survivors, hyperoxia was associated with a lower proportion of functional independence at discharge compared to patients with normoxia (29% vs. 38%, respectively; proportion difference, 9% [95% CI, 3%-15%]).

Figure 4: In-hospital death between hyperoxia and normoxia groups.

C.3.2. Dose-dependent relationship between supranormal PaO₂ and risk of death after cardiac arrest.

Kilgannon JH, Jones AE, Parrillo JE, Dellinger RP, Milcarek B, Hunter K, Shapiro NI, Trzeciak S.

[figure not shown]
Relationship between supranormal oxygen tension and outcome after resuscitation from cardiac arrest.

Circulation 2011; 123(23):2717-22.

Using the same ICU database, we tested the hypothesis that a linear, dose-dependent relationship exists between post-resuscitation supranormal oxygen tension (highest PaO₂ over the first 24 hours in the ICU) and in-hospital mortality. Among 4459 patients, the median PaO₂ was 231 (IQR 149-349) mmHg. Over ascending ranges of oxygen tension, we found significant linear trends of increasing in-hospital mortality and decreasing survival as functionally independent, $p < 0.0001$ (**Figure 5**). On multivariable analysis, a 100 mmHg increase in PaO₂ was associated with a 24% increase in mortality risk (odds ratio 1.24 [95% CI 1.18-1.31]) (**Figure 6**).

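### The REOX II versus REOX I comparison of mRS 3 or below is unadjusted between non-randomised groups and leaves out the 0-hour PaO2 that every site already measures

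*Combined protocol and SAP*

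**What the plan says.** D.1.2 (Overview) describes a protocol implementation study comparing REOX II with the observational REOX I, and gives mRS 3 or below at discharge as the primary outcome. Under Therapeutic interventions in D.2, "subjects in REOX I (observational only component) had clinician-directed FiO₂ titration after ROSC". No eligibility criterion concerns PaO2.

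The analysis section opens with a pooled regression of mRS, treated as continuous, on time-weighted average PaO2 over the first 24 hours. The listed covariates are Charlson index, downtime over 20 minutes, initial rhythm, arrest location and PaO2/FiO2 below 100. Group is not a term in that model. The comparison of mRS 3 or below between patients who did and did not receive the protocol comes under Secondary analyses, as a binomial test with no covariates.

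Data collection states: "As part of standard care each institution already obtains ABG analyses at 0- and 6-hours after ROSC". Informed consent and Therapeutic interventions allow activation only after written surrogate consent, which must be obtained within four hours of ROSC. Patients without consent in that time may join the observational component.

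The Sample Size section derives 280 from the cognitive-domain regressions and sets REOX II as what is left: "plan for 75 subjects to be enrolled in REOX II to ensure a total sample size of at least 280 subjects".

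**The concern.** The two groups differ by calendar period and by whether a surrogate was reached within four hours. Nothing in the design balances their oxygenation at ROSC. If one group starts with a higher PaO2, the unadjusted test attributes the consequence to the protocol or hides a benefit of it. The measurement needed to deal with this is already taken, before the protocol can affect it.

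The second issue is how a null result would be read. The rationale in C.3.1 compares extremes: "patients with hyperoxia had significantly higher in-hospital mortality (63% [95% CI 60%-66%]) compared to patients with normoxia" (45%). The study compares a protocol with usual titration, which includes patients across the whole PaO2 range. The expected difference is smaller, and no power is stated for it.

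**Working it through.** **1. What the stated power covers.** Inputs from Sample Size: R² = 0.15, six predictors, alpha 0.05.
- f² = 0.15/0.85 = 0.1765. With n = 85 the noncentrality is 85 × 0.1765 = 15.0, on 6 and 78 degrees of freedom, and power is 80.8%. The plan's 85 reproduces.
- 85 × 1.15 = 97.75, or 98; 98/0.35 = 280. The plan's total reproduces.
- The 80% therefore belongs to the cognitive-domain regressions among tested survivors. The section says the initial proposal's 266 was based on mRS, but gives no effect size or power for it.

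**2. Use of the 0-hour gas.** The 0-hour value precedes activation by construction. The 6-hour gas falls after the consent window has closed. Of the planned analyses:
- the binomial test has no covariates;
- the time-weighted regression includes early gases only as part of a 24-hour average that also contains values the protocol has changed.

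Neither compares protocol and non-protocol patients who started at the same PaO2.

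**3. Possible size of the bias.** Assume that the C.3.2 odds ratio of 1.24 per 100 mmHg applies to 0-hour PaO2, and start from the 45% mortality of the normoxic group. The odds are 0.45/0.55 = 0.818.
- Imbalance of 50 mmHg: 0.818 × 1.24^0.5 = 0.911, or 47.7%, a shift of 2.7 points.
- Imbalance of 100 mmHg: 0.818 × 1.24 = 1.015, or 50.4%, a shift of 5.4 points.

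The imbalances are assumed; the documents give no REOX I PaO2 data. The shift could go either way.

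**4. Strength of the group contrast.** Power is computed by enumerating both binomials at 205 versus 75, with a pooled z-test at two-sided 5%. Mortality stands in for mRS because no expected mRS rates are given.
- Hyperoxia versus normoxia throughout, 63% versus 45%: 77%.
- Dose-response. C.3.2 reports that "the median PaO₂ was 231 (IQR 149-349) mmHg". Assume a fall from 231 to 80 mmHg (the target in C.3.3 is 60 to 99). The odds ratio is 1.24^1.51 = 1.38. From 45% under the protocol, the comparator is at 53.1%, a difference of 8.1 points and power of about 23%. From 60% in the comparator, the protocol group is at 52.0%, a difference of 8.0 points and again about 23%.
- Threshold model. 300 mmHg lies between the median (231) and the upper quartile (349), so between 25% and 50% of that cohort reached it. If only those patients benefit, comparator mortality is 0.45 + 0.18h, where h is their share:

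| h | Comparator mortality | Difference (points) | Power |
|---|---|---|---|
| 25% | 49.5% | 4.5 | 10% |
| 35% | 51.3% | 6.3 | 15% |
| 50% | 54.0% | 9.0 | 27% |

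**5. Would a stratum at 300 mmHg or more rescue it?** Keeping the full 18 points there, power is 28% (51 versus 19 patients, h = 25%) to 49% (102 versus 38, h = 50%). A test of interaction across that cut-off has about 21% to 27% by normal approximation.

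**The case against.** Usual care is a legitimate comparator for a protocol implementation study. The effect of introducing a protocol across all eligible patients is a sensible question, and including those with modest PaO2 is part of it. The first-described model uses actual exposure and is not diluted in this way. The group contrast is labelled secondary, and the Sample Size section already ties 280 to the multivariable testing. Nowhere does the plan say that a null contrast would be read as no effect. All of this stands, so the choice of comparator is not an error.

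A reader might go further and infer that at most half the comparator was hyperoxic, that the protocol could not help the rest, and that only patients at 300 mmHg or more answer the question. The documents do not support this:
- The 25% to 50% share comes from another cohort, on a different measure: "highest PaO₂ over the first 24 hours in the ICU". It omits the emergency department phase and is not a 0-hour gas.
- The 300 mmHg cut-off belongs to the team's earlier studies. The REOX analysis section sets none and states a preference for continuous measures.
- The protocol aims at 60 to 99 mmHg. The lower quartile of the database peaks is 149, so more than 75% exceeded the target, and C.3.2 reports a linear dose-response. Patients below 300 mmHg may well benefit.

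It is also fair to say that clinicians may lower FiO2 between the 0-hour gas and activation, so this gas is an imperfect marker of who stands to gain. It remains a valid pre-activation covariate. The objection does not answer the lack of adjustment: the time-weighted regression has no group term and mixes values from before and after activation.

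**Conclusion.** The point holds as one of adjustment and interpretation. The only between-group test of the stated primary outcome is unadjusted in non-randomised groups and ignores a baseline value already collected. An imbalance of 50 to 100 mmHg could move the contrast by roughly 3 to 5 points, against an expected difference of about 8 under the team's own dose-response.

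Power for the contrast is about 23% on that dose-response, or 10% to 27% on the threshold model, against 77% for the difference behind the rationale. These are illustrations. They rest on observational database mortality standing in for mRS, on an assumed fall to 80 mmHg or an effect confined to 300 mmHg and above, and on REOX I resembling the database. The threshold model also puts all other patients at 45%, although C.3.1 reports 57% for hypoxia. A null group contrast would be weak evidence either way.

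**What to change.** In Secondary analyses:
1. Replace the binomial test of mRS 3 or below with a logistic regression on group, adjusted for continuous 0-hour PaO2 and the five covariates already listed. Check the PaO2 term for curvature, since C.3.1 shows higher mortality at both ends (57% hypoxia, 45% normoxia, 63% hyperoxia). State how missing 0-hour gases are handled. Take PaO2/FiO2 from the 0-hour gas too, as the plan gives no time for it.
2. Add an exploratory interaction of group with continuous 0-hour PaO2, reported as an estimate with its interval. 300 mmHg may serve as a reporting point, not as the decisive stratum.
3. Report the 0-hour PaO2 distribution in REOX I, starting with the 200 patients already enrolled.
4. State that the 80% power covers only the cognitive-domain regressions, and that a null group contrast will be reported as an estimate with its interval.

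The cost is SAP wording and slightly more analysis on gases already taken. The model has seven terms, or eight with the interaction. The plan's 35% at mRS 4 or below gives 0.35 × 280 = 98 patients, so good outcomes number at most about 98, which limits further terms. Power for the interaction will be low, and the SAP should say so.
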